## 5.2. Study Treatment Administration

All IMP vials will be removed from storage at 2°C to 8°C for between 5 to 60 minutes prior to dose preparation. The IMP vials will be swirled for approximately 3-5 seconds, IMP will be drawn up into 1 or more BD tuberculin syringes (0.3 or 1.0 mL), and syringes containing IMP will be used within 6 hours after dose preparation. Each dose of CPT31 and placebo will be administered by SC injection into the abdomen while the subject is in a semi-supine or sitting position. Subjects will be fasted for at least 8 hours prior to dosing and for at least 2 hours after dosing; a meal will be provided after the 2-hour postdose assessments are completed.

Subjects will be administered the IMP while semi-supine or seated and will remain semi-supine or seated for at least 30 minutes after dosing, except as necessitated by the occurrence of an AE(s) and/or study procedures.

The doses and estimated injection volumes are detailed in [Table 4](#). Rounding may be used based on measurable volumes in the appropriate syringe.

**Table 4: Injection Volumes**

Group	Dose Level (mg/kg)	Frequency	Estimated Injection Volume a (mL)
A1	0.01	Once	0.047
A2	0.04	Once	0.187
A3	0.12	Once	0.56
A4	0.24	Once	1.12

a Assuming a 70 kg subject.

## 5.3. Randomization

The randomization code will be produced by the Statistics Department at Covance using a computer-generated pseudo-random permutation procedure. Two subjects per group will be randomly assigned to receive placebo. For all groups, sentinel dosing will occur whereby 2 subjects (1 active and 1 placebo) will be dosed on 1 day and, providing no safety concerns arise, the remaining 6 subjects (5 active and 1 placebo) will be dosed after 72 hours.

Prior to the start of the study, the live randomization will be distributed according to the randomization specification form and will include the Covance CRU pharmacy staff.

## 5.4. Blinding

The following controls will be employed to maintain the double-blind status of the study:

- The placebo solution may not be identical in appearance to the CPT31 solution. The unblinded pharmacy staff member will prepare syringes for injection (placebo and CPT31 solution) and an unblinded study nurse will perform the injections. If color differences are apparent between active and placebo in dosing syringes, then subjects will be blindfolded prior to and during study drug/placebo injection. Other Covance staff, e.g., CRCs, will be asked to avert their eyes during study drug/placebo injection.

- The Investigator and other members of staff involved with the study will remain blinded to the treatment randomization code during the assembly procedure.
- Interim bioanalytical data will be provided to the PSRT in a blinded manner.

To maintain the blind, the Investigator will be provided with a sealed randomization code for each subject, containing details of their treatment. These individual sealed envelopes will be kept in a limited access area that is accessible 24 hours a day. In order to manage subject safety or to support dose escalation decisions (in the event of possibly treatment-related SAEs or Grade  $\geq 3$  AEs), the decision to unblind resides solely with the Investigator. Whenever possible and providing it does not interfere with or delay any decision in the best interest of the subject, the Investigator will discuss the intended code-break with the Sponsor. If it becomes necessary to break the code during the study, the date, time, and reason will be recorded in the subject's source data and on the individual envelope and will be witnessed by a second person.

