### **2.2. Endpoints**

#### **2.2.1. Primary Endpoints**

The primary safety endpoints for this study are as follows:

- incidence and severity of adverse events (AEs)
- incidence of laboratory abnormalities, based on hematology, clinical chemistry, and urinalysis test results

- 12-lead electrocardiogram (ECG) parameters
- vital signs measurements
- physical examinations
- anti-CPT31 antibodies, e.g., immunoglobulin (Ig)G, IgM

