### **3.1. Overall Study Design and Plan**

This study will comprise a placebo-controlled, double-blind, single-dose, sequential-group design. Overall, it is planned for 32 healthy subjects to be studied in 4 groups (Groups A1 to A4), with each group consisting of 8 subjects. In each group, 6 subjects will be randomized to receive SC CPT31 and 2 subjects will be randomized to receive matching placebo.

Potential subjects will be screened to assess their eligibility to enter the study within 28 days prior to the first dose administration.

Each subject will participate in 1 treatment period only. Subjects will reside at the Clinical Research Unit (CRU) from Day -1 (the day before dosing) to Day 6. All subjects will return for a Follow-up visit 28 to 30 days after dosing.

Based on the ongoing review of the safety, tolerability, and PK results, additional nonresidential visits may be required. The number of additional visits per subject will not exceed 3 and will not extend beyond 30 days after dose administration.

[figure not shown]
All groups will be divided into 2 cohorts, with each cohort being dosed 72 hours apart. The first (sentinel) cohort will comprise 2 subjects, with 1 subject receiving CPT31 and 1 subject receiving placebo. The second cohort will comprise 6 subjects, with 5 subjects receiving CPT31 and 1 subject receiving placebo.

The maximum total duration of study participation for each subject (from Screening through Follow-up visit) is anticipated to be approximately 8 weeks.

Dose escalation will occur a minimum of 7 days after all subjects complete all Day 6 assessments in the previous dose group.

[figure not shown]
An overview of the study design is shown in [Figure 1](#) and the planned dose levels in are shown in [Figure 2](#). A Schedule of Assessments is presented in [Appendix 6](#).

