### Assessment of Severity

The Investigator will be asked to provide an assessment of the severity of the AE using the following criteria defined by the Division of AIDS Table for Grading the Severity of Adult and Pediatric Adverse Events, Version 2.1 dated July 2017:

- **Grade 1, Mild:** Usually transient and may require only minimal treatment or therapeutic intervention. The event does not generally interfere with usual activities of daily living.
- **Grade 2, Moderate:** Usually alleviated with additional specific therapeutic intervention. The event interferes with usual activities of daily living, causing discomfort but poses no significant or permanent risk of harm to the subject.
- **Grade 3, Severe:** Interrupts usual activities of daily living, or significantly affects clinical status, or may require intensive therapeutic intervention.
- **Grade 4, Potentially Life-threatening:** The subject was at immediate risk of death from the event as it occurred (i.e., does not include a reaction that might have caused death if it had occurred in a more serious form). For instance, drug-induced hepatitis that resolved without evidence of hepatic failure would not be considered life-threatening even though drug-induced hepatitis can be fatal.
- **Grade 5, Death.**

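### The placebo may look different from CPT31, yet no syringe is covered and the unblinded injecting nurse is not kept out of adverse event assessment

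*Protocol*

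**What the plan says.** Protocol Section 3.1 states that in each group "2 subjects will be randomized to receive matching placebo"; the Synopsis and SAP Section 4 also call the placebo matching. Section 5.4 is more guarded: "The placebo solution may not be identical in appearance to the CPT31 solution."

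The controls against a visual leak, all in Section 5.4, are these:

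- An unblinded pharmacy staff member prepares the syringes, and "an unblinded study nurse will perform the injections".
- For subjects: "If color differences are apparent between active and placebo in dosing syringes, then subjects will be blindfolded prior to and during study drug/placebo injection."
- For other site staff: "Other Covance staff, e.g., CRCs, will be asked to avert their eyes during study drug/placebo injection."

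Section 5.4 also provides sealed individual codes held under limited access, a witnessed and documented code-break, and blinded delivery of interim bioanalytical data to the Protocol Safety Review Team. Section 3.4 gives the reason for the blind, which is to keep bias out of the collection and evaluation of data.

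**The concern.** Using an unblinded injector is a sound answer to products that look different, provided two things hold: nobody who assesses subjects can see the syringe, and whoever has seen it does not assess. The plan makes the first depend on staff looking away and does not state the second.

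At stake is the part of the safety evaluation that rests on judgment. AE incidence and severity and physical examination are listed primary endpoints (Protocol Section 2.2.1). Relatedness is not a listed primary endpoint, but it defines the treatment-related AE tables in SAP Section 8.6.1. It also feeds the SAE and Grade 3/4 criteria in Protocol Section 3.7 and the Grade 3/4 criterion in Section 3.8. Someone who knows or guesses the allocation may ask, record or attribute differently for CPT31 and placebo subjects.

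**Working it through.** The plan states no figure on this point, so the check is mainly a comparison of texts, with a short calculation of what a glimpse would reveal.

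**1. What is masked, and from whom (Protocol Section 5.4).** Unblinded preparation and injection are unconditional. The blindfold is conditional: it is triggered by color alone, and no one is named to judge whether a difference is apparent. The eye-averting sentence has no condition of its own, although it follows the conditional one, and it is only a request. Neither document mentions an opaque sleeve, a screen or a restriction on who is in the room. Section 5.5 requires doses to be given under supervision of qualified site staff; unless the unblinded nurse is that supervisor, this sits awkwardly with looking away.

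**2. Who makes each judgment.**

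- AE questioning (Protocol Section 7.3.1): open questions at least daily during residence; no role assigned.
- Physical examination (Section 7.3.5 and Appendix 6): symptom-directed after dosing; no role assigned.
- Severity (Appendix 1): "The Investigator will be asked to provide an assessment of the severity of the AE."
- Causality (Appendix 1): the investigator or a designee; no requirement that the designee be blinded.

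The schedule in Appendix 6 has no separate injection-site assessment, so local reactions reach the data through the first two steps. The routes open to an unblinded nurse are therefore elicitation, examination and designated causality rating. Severity is the investigator's task and would be affected through a visual leak or through what is elicited.

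**3. What a glimpse reveals.** Inputs from Sections 3.1 and 5.3: 4 groups, each with a sentinel cohort of 1 active and 1 placebo and a second cohort of 5 active and 1 placebo. Check: 4 × (6 + 2) = 32 subjects, of whom 4 × 6 = 24 are active and 4 × 2 = 8 placebo, as planned.

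With the blind intact, the chance that a given subject is on CPT31 is 5/6 = 0.83 in the second cohort and 1/2 in the sentinel cohort. If the solutions do differ visibly:

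- *Second cohort, one syringe seen, appearance not known beforehand:* nothing to compare, so the chance stays at 5/6.
- *Second cohort, the single placebo syringe recognised:* the other five must be active, so all 6 of 6 are identified.
- *Second cohort, an active syringe recognised by someone who knows its appearance:* that subject is identified; among the other five, 4/5 = 0.80 are active.
- *Sentinel pair, two different-looking syringes, appearance not known:* the difference shows but not which is which. If one is recognised, both subjects are identified.

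**4. How visible a difference might be.** Table 4 volumes follow from dose × 70 kg ÷ 15 mg/mL: 0.01 × 70 ÷ 15 = 0.047 mL in A1, then 0.187, 0.56 and 0.24 × 70 ÷ 15 = 1.12 mL in A4. A tint hard to see at 0.047 mL could be plain at 1.12 mL, so the blindfold trigger might be met in some groups and not in others. That is inference; the documents do not describe the actual appearance.

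**5. Which endpoints are exposed.** Of the primary endpoints in Section 2.2.1, AE incidence and severity and physical examination involve judgment. Laboratory tests, ECG, vital signs and antibodies are largely objective.

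**The case against.** The strongest reply is that the omission is one of detail. Nothing says the nurse will rate anything, severity is assigned to the investigator, and if no color difference appears, no color-based leak arises. All of this is true. But Section 5.4 itself raises the possibility of a difference, and neither document refers to a site procedure that closes the gap.

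It can also be said that over-attribution to CPT31 would stop escalation sooner, which is the cautious direction, that the liver and renal criteria are numeric and confirmed by repeat testing, and that the investigator may break the code to support escalation decisions after possibly related SAEs or events of Grade 3 or above. The numeric rules are indeed largely protected. For the others, the relatedness rating comes before any code-break, and the SAP's AE tables would carry a bias in either direction.

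Three stronger readings are tempting and are not supported:

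- A reader might infer that staff are blinded only while doses are prepared, because Section 5.4 says they "will remain blinded to the treatment randomization code during the assembly procedure". Read whole, the section lists controls to keep the study double-blind and adds sealed codes and controlled code-breaks. The wording is awkward but does not limit the blind.
- A reader might infer that one glimpse unblinds a cohort, or that an appearance learned in A1 classifies everyone afterwards. The first requires recognising the placebo syringe. The second requires each later syringe to be seen despite averted eyes, although the common 15 mg/mL solution would let a known appearance carry forward.
- A reader might infer that each group's results rest on 2 placebo subjects. SAP Table 1 has one placebo column, so the tabulated comparator is the pooled 8.

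**Conclusion.** The point holds as an inexpensive improvement to Section 5.4. It does not show that the blind failed, or that the primary safety evaluation as a whole is compromised. What stands is that a possible difference in appearance is acknowledged, the masking against it is weak, and the person certain to know the allocation is not separated from assessment.

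Its reach is limited to AE incidence and severity, physical examination, and the relatedness ratings behind the treatment-related AE tables and the SAE and Grade 3/4 criteria. Recognising the one placebo syringe in a second cohort would expose all six subjects. The documents contain nothing from which to estimate how far ratings would shift. The safety analysis is descriptive, so no error rate or power is affected; the exposure is the reading of 24 active against 8 pooled placebo subjects and the judgment-based stopping criteria. The conclusion assumes that the solutions do differ visibly in at least some syringes and that no unreferenced site procedure already separates the roles.

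**What to change.** Amend Protocol Section 5.4 as follows:

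1. After the volume check, the unblinded pharmacy staff member puts an opaque sleeve or label on every CPT31 and placebo syringe, in all groups. Section 5.2 allows more than one syringe per dose, so each one is covered.
2. The subject's view is shielded if there is any visible difference, not only one of color.
3. The unblinded preparer and injector take no part in AE questioning, injection-site or physical examination, or severity or causality rating, including as designee, and do not disclose allocation to assessors. Vital signs and ECG need not be barred, since they are largely objective.
4. Reconcile 'matching' in the Synopsis, Section 3.1 and SAP Section 4 with Section 5.4, by deleting or qualifying the word.

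The cost is protocol wording, sleeves or labels, a minute or two per dose and a small roster constraint. The staff needed are already in the plan, and no dose, schedule, sample size or stopping rule changes.

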### **5.5. Treatment Compliance**

The following measures will be employed to ensure treatment compliance:

- All doses will be administered under the supervision of suitably qualified study site staff.
- At each dose preparation occasion, a predose and postdose inventory of IMP will be performed.

### **5.6. Drug Accountability**

The Investigator (or designee) will maintain an accurate record of the receipt of the study supplies received. In addition, an accurate drug disposition record will be kept, specifying the amount dispensed to each subject and the date of dispensing. This drug accountability record will be available for inspection at any time. At the completion of the study, the original drug accountability record will be available for review by the Sponsor upon request.

Empty or partially used IMP vials will be discarded upon satisfactory completion of the compliance and accountability procedures. Any unused IMP vials will be retained until completion of the study.

At the completion of the study, all unused supplies will be returned to the Sponsor or disposed of by the study site, per the Sponsor's written instructions.

## **6. CONCOMITANT THERAPIES AND OTHER RESTRICTIONS**

### **6.1. Concomitant Therapies**

Subjects will refrain from use of any prescription or nonprescription medications/products (including HIV medications being used for pre-exposure prophylaxis) within 14 days of dosing, unless the Investigator (or designee) and/or Sponsor have given their prior consent.

Paracetamol/acetaminophen (2 g/day for up to 3 consecutive days), hormone replacement therapy, oral, implantable, transdermal, injectable, or intrauterine contraceptives are acceptable concomitant medications. The administration of any other concomitant medications during the study is prohibited without prior approval of the Investigator (or designee), unless its use is deemed necessary for treatment of an AE. Any medication taken by a subject during the course of the study and the reason for its use will be documented in the source data.

All concomitant medications, over-the-counter preparations, vitamins and nutritional supplements, recreational drugs, and herbal preparations reported throughout the course of the study will be recorded in the source documents and on eCRFs designated for that purpose.

## **6.2. Diet**

While confined at the study site, subjects will receive a standardized diet at scheduled times that do not conflict with other study-related activities. Subjects will be fasted overnight (at least 8 hours) before collection of blood samples for clinical laboratory evaluations that include the lipid panel (see [Appendix 6](#)).

On the days with intensive PK assessments (Day 1), meals will be identical for each group.

On Day 1, subjects will be fasted for at least 8 hours prior to dosing, and at least 2 hours after dosing; a light breakfast will be provided after the 2-hour postdose assessments are completed. Breakfast time will be staggered between subjects to ensure that it is taken at the same time with respect to dosing.

Meals will be provided as appropriate at other times. Water will be freely available at all times.

Caffeine-containing foods and beverages will not be allowed from 48 hours before Day -1 until Discharge.

Consumption of alcohol will not be permitted from 72 hours prior to Day -1 until the Follow-up visit.

## **6.3. Smoking**

Subjects will not be permitted to use tobacco- or nicotine-containing products within 3 months prior to Day -1 until the Follow-up visit.

## **6.4. Exercise**

Subjects are required to refrain from strenuous exercise from 7 days before Day -1 until the Follow-up visit and will otherwise maintain their normal level of physical activity during this time (i.e., will not begin a new exercise program nor participate in any unusually strenuous physical exertion).

## 6.5. Blood Donation

Subjects are required to refrain from donation of blood from 3 months prior to Screening, plasma from 2 weeks prior to Screening, and platelets from 6 weeks prior to Screening until 3 months after the Follow-up visit.

## 7. STUDY ASSESSMENTS AND PROCEDURES

Every effort will be made to schedule and perform the procedures as closely as possible to the nominal time, giving considerations to appropriate posture conditions, practical restrictions, and the other procedures to be performed at the same timepoint.

The highest priority procedures will be performed closest to the nominal time. The order of priority for scheduling procedures around a timepoint is (in descending order of priority):

- dosing
- blood samples
- urine samples (for CPT31 assay, males only)
- any other procedures (ECGs will be scheduled before vital signs measurements).

Where activities at a given timepoint coincide, consideration must be given to ensure that the following order of activities is maintained: ECGs, vital signs, blood draws.

### 7.1. Pharmacokinetic Assessments

#### 7.1.1. Sample Collection and Processing

Blood samples (approximately  $2 \times 1$  mL) will be collected by venipuncture or cannulation at the times indicated in the Schedule of Assessments in [Appendix 6](#). Furthermore, up to 3 additional blood samples may be taken from each subject, with the maximum volume of blood withdrawn per subject not exceeding the limit detailed in [Appendix 3](#). Any changes to the scheduled times of PK assessments will be agreed with the Sponsor and documented in the TMF. Samples taken from subjects who received placebo will not be analyzed.

Procedures for collection, processing, and shipping of PK blood samples will be detailed in a separate document.

Urine samples, for male subjects only, will be collected into pre-weighed polyethylene containers over the time intervals indicated in the Schedule of Assessments in [Appendix 6](#). Procedures for collection, processing, and shipping of urine samples will be detailed in a separate document.

#### 7.1.2. Analytical Methodology

Plasma and urine concentrations of CPT31 will be determined using validated analytical procedures. Specifics of the analytical methods will be provided in separate documents.

## **7.2. Immunogenicity Assessments**

Blood samples (approximately  $2 \times 1$  mL) will be collected by venipuncture or cannulation at the times indicated in the Schedule of Assessments in [Appendix 6](#). The timings may be subject to change based on the ongoing review of the data.

## **7.3. Safety and Tolerability Assessments**

### **7.3.1. Adverse Events**

Adverse event definitions, assignment of severity and causality, and procedures for reporting SAEs are detailed in [Appendix 1](#).

The condition of each subject will be monitored from the time of signing the ICF to final discharge from the study. Subjects will be observed for any signs or symptoms and asked about their condition by open questioning, such as “How have you been feeling since you were last asked?”, at least once each day while resident at the study site and at each study visit. Subjects will also be encouraged to spontaneously report AEs occurring at any other time during the study.

All nonserious AEs, whether reported by the subject voluntarily or upon questioning, or noted on physical examination, will be recorded from initiation of study drug until study completion. Serious AEs will be recorded from the time the subject signs the ICF until study completion. The nature, time of onset, duration, and severity will be documented, together with an Investigator’s (or designee’s) opinion of the relationship to study drug. Photos may be taken of visible side effects, such as a skin rash, for the study records.

Adverse events recorded during the course of the study will be followed up, where possible, until resolution or until the unresolved AEs are judged by the Investigator (or designee) to have stabilized. This will be completed at the Investigator’s (or designee’s) discretion.

